##### **14.4.1. Deaths**

All deaths, regardless of causality, will be provided in listings and written clinical narratives.

##### **14.4.2. Serious Adverse Events**

The number and percent of subjects with Serious Adverse Event (SAE) will be displayed by system organ class and preferred term, and relationship to study medication. Within each preferred term, subjects will be counted only once if they had more than one SAE event reported during the treatment period.

Clinical narratives for each SAE observed will be written to include important data and safety findings related to the individual SAE and included in the final clinical study report.

##### **14.4.3. Adverse Events Leading to Discontinuation of Study Drug Injection**

The number and percent of subjects with AE's leading to discontinuation, or interruption, of study drug will be displayed by system organ class and preferred term for each treatment group. Within each preferred term, subjects will be counted only once if they had more than one AE leading to discontinuation, or interruption, of study drug reported during the treatment period.

A listing will be produced for all subjects who reported serious TEAEs or who discontinued study medication due to TEAEs.

#### **14.5. Clinical Laboratory Evaluations**

In addition to categorical and continuous descriptive analyses as noted earlier, scatter plots of the baseline value (x-axis) and end of study (y-axis) will be completed for each clinical laboratory parameter. Reference ranges will be highlighted on the plots to identify laboratory assessments that are out of range.

#### **14.6. Physical Examinations**

Physical examination results will be listed by subject for baseline and end of study assessment. Changes in physical examination from baseline to end of study will be recorded as adverse events.

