8.5 Safety Evaluation

8.5.1 Safety Parameters

Safety parameters to be measured/assessed include eligibility assessments, medical history, vital signs, physical examinations, clinical laboratory tests, and pregnancy tests. Any abnormal hematology, serum chemistry, serum lipid, or urinalysis parameters considered clinically significant by the Investigator will be captured as AEs.

Subjects will be monitored throughout the study for AEs, as well as for changes in clinical status, vital signs, and laboratory data. Any non-serious AEs occurring from the time the ICF and Assent forms, if required, are signed until just prior to receiving the first injection of study drug will be considered as non-TEAEs unrelated to study drug administration.

Serious adverse events (SAEs) that occur as a result of study-mandated procedures during the time period after the ICF and Assent forms are signed, as appropriate, but prior to receiving the first injection of study drug will be collected but not designated as TEAEs.

In order to evaluate changes in the acute (within two weeks of administration) and chronic hormonal responses associated with GnRH antagonist treatments over time, subjects (or their parents/guardians) will be asked two weeks (14 days \pm 2 days) after every study drug administration (by telephone contact), and at each scheduled visit, the following question(s):

- How have you felt in the last two weeks?

or alternatively (if the parent or guardian is answering on behalf of the subject)

- How has your child felt in the last two weeks?

Investigators will record any adverse events that are reported at that time.

In addition the investigators will categorize the more specific responses that have been identified in the table ([Table 4](#)), which are often associated with GnRH antagonist injectable treatments. If the subject (or parent/guardian) does not report any condition (within the last two weeks) that fits into the [Table 4](#) categories, the Investigator will check the response that no conditions associated with GnRH antagonists were reported (“NO”). If any of the conditions reported by the subject (or parent/guardian) fit into one (or more) of the categories, then the Investigator will check “YES” for each applicable category. This reported information will be collected by completing [Table 4](#):

Table 4 GnRH Antagonist Evaluations

Any GnRH antagonist conditions reported?	Yes/No
If the answer is “Yes”, please categorize as described below:	

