8.5.4 Definition of Terms

8.5.4.1 Adverse Event Definition

An AE is defined as any untoward medical occurrence associated with the use of a drug in humans, whether or not considered drug related (21 CFR 312.32 (a)). An AE can, therefore, be any unfavorable and unintended sign (eg, an abnormal laboratory finding considered clinically significant by the Investigator), symptom, or disease temporally associated with the use of a drug, without any judgment about causality. For this protocol, any unfavorable and unintended sign, symptom, or disease occurring after signature of Informed Consent/Assent will be collected as AEs.

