8.5.5 Reporting of Adverse Events

All AEs that are observed by the Investigator or one of his/her medical collaborators, or reported by the subject, will be reported even if they are potentially attributable to unrelated medical

conditions or other medications the subject may be taking. The information recorded for AEs will include start date, a description of the AE, severity, causal relationship to Investigational Product/study drug, action taken, outcome of the event (including any treatment and/or hospitalization), and stop date. In addition, start time will be collected for events beginning on the day of the first injection.

Medical conditions or diseases present before a subject is enrolled in the study are only considered AEs if they worsen after the subject is enrolled.

For each AE, the seriousness, severity, and causal relationship to study drug will be assessed and entered in the source document. All items on the AE page of the eCRF should be completed for each AE.

Surgical procedures themselves are not AEs; they are therapeutic measures for conditions that require surgery. The condition for which the surgery is required is an AE, if it occurs or is detected during the study period. Planned surgical measures and the conditions leading to these measures are not AEs, if the condition(s) was (were) known before the study treatment. In the latter case, the condition should be reported as medical history.

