8.6.10 Part A, Visit 7 (~Month 11/Week 44 ± 7 days)

NOTE: DO NOT complete Part A, Visit 7, if a decision has been made to conduct Part B extension study. In this case, follow procedures for Part B (Visits 7 to 13) beginning in [Section 8.6.12](#).

1. Query subject or parent: “How have you felt in the last two weeks?” or “How has your child felt in the last two weeks?” Complete [Table 4](#)
2. Vital signs - measured prior to any blood draws
3. Height and weight
4. AE and concomitant medications assessments
5. Blood samples for basal LH, FSH, testosterone/estradiol concentrations
6. Blood sample for basal serum leuprolide concentrations
7. Schedule/confirm next visit

8.6.11 Part A, Visit 8 (~Month 12/Week 48 ± 7 days) End of Treatment or Early Discontinuation

1. Query subject or parent “How have you felt in the last two weeks?” or “How has your child felt in the last two weeks?” Complete [Table 4](#)
2. Vital signs – measured prior to any blood draws
3. AE and concomitant medications
4. Physical Examination-complete
5. Tanner stage
6. Height and weight
7. X-ray of non-dominant hand and wrist
8. Urine pregnancy test, females only
9. Clinical laboratory assessments (hematology, chemistry) as per [Appendix 13.1](#)
10. Urine for urinalysis, performed using dipstick supplied by Sponsor
11. Blood samples for basal LH, FSH, testosterone/estradiol concentrations PRIOR to the GnRHa stimulation test
12. Blood sample for serum leuprolide concentrations PRIOR to the GnRHa stimulation test
13. GnRHa stimulation: aqueous leuprolide acetate 20 µg/kg body weight administered SC
14. Blood samples for LH, FSH, testosterone/estradiol concentrations 30 ± 5 minutes AFTER the GnRHa stimulation test

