#### **8.1.7. Physical Examination**

A complete physical exam (PE) will be performed by study personnel who are qualified to perform such examinations. At a minimum, the PE should include the cardiovascular system, the respiratory system, and the abdomen.

Thereafter, a directed or targeted PE will be performed covering body systems related to the disease, including Tanner stages, and/or to assess any ongoing AEs.

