### **8.2.2. Secondary Efficacy Endpoints and Assessments**

Serving as secondary endpoints will be the following variables.

- The percentage of subjects with serum LH concentrations < 4 mIU/mL at 30 minutes following an abbreviated GnRHa Stimulation Test for any available measurement other than the measurement constituting the primary outcome variable (see above).
- The percent change from baseline in height at each available post-baseline measurement. Percent change is defined as  $((\text{change from Baseline})/(\text{Baseline})) \times 100$ .
- The growth velocity of height in cm/year at each available post-baseline measurement. Growth velocity is defined for each visit as  $(\text{change from Baseline})/[(\text{number of weeks since Baseline})/52]$ .
- The ratio of bone age at each given measurement point to chronological age at the same measurement points.
- Baseline to end-of-study stage shifts for each Tanner category.
- The percent change from baseline in hormonal concentration (LH, FSH, Testosterone, and Estradiol) at each available post-baseline measurement. Percent change is defined as  $((\text{change from baseline})/(\text{baseline})) \times 100$ .
- The percent change from baseline in systemic leuprolide concentration at each available post-baseline measurement. Percent change is defined as  $((\text{change from baseline})/(\text{baseline})) \times 100$ .

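### SAP 14.6 turns any change in physical examination from baseline to end of study into an adverse event, so a resolved or improved finding would be counted, contrary to the protocol's AE definition

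*SAP*

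**What the plan says.** SAP 14.6 first has examination results listed by subject for baseline and end of study, then states: "Changes in physical examination from baseline to end of study will be recorded as adverse events". It does not require the change to be a worsening, to be new, or to be judged adverse by anyone.

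The protocol is narrower in three places:

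- **AE definition (8.5.4.1):** "any unfavorable and unintended sign, symptom, or disease occurring after signature of Informed Consent/Assent will be collected as AEs".
- **Conditions present before enrolment (8.5.5):** they "are only considered AEs if they worsen after the subject is enrolled".
- **Laboratory results (8.5.1):** "Any abnormal hematology, serum chemistry, serum lipid, or urinalysis parameters considered clinically significant by the Investigator will be captured as AEs".

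On examination content, SAP 8.1.7 says of the complete examination: "At a minimum, the PE should include the cardiovascular system, the respiratory system, and the abdomen". It then says that "a directed or targeted PE will be performed covering body systems related to the disease, including Tanner stages". Protocol 8.4.8 has the same two statements. Tanner change has its own place in SAP 8.2.2, as a secondary efficacy endpoint: "Baseline to end-of-study stage shifts for each Tanner category".

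**The concern.** An examination finding can move in either direction between baseline and end of study. A rule that turns movement in both directions into AEs mixes recovery with harm. It also departs from the definition the investigators are told to use.

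What is at stake is the safety tabulation. Safety and tolerability is a secondary objective in both documents (Protocol 7.2, SAP 5.2). The study has a single arm, so there is no control group in which a spurious excess of AEs would show itself. SAP section 4 also allows procedures in the final SAP to be cited as specified in advance, so a table built on the 14.6 rule could be presented as the planned analysis.

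**Working it through.** No formula applies, and there is no figure in the plan to reproduce. The check sets the rules side by side and follows one finding through each.

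**Step 1. Classify the possible changes.**

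| Finding, baseline to end of study | SAP 14.6 as written | Protocol 8.5.4.1 and 8.5.5 |
|---|---|---|
| Normal, then abnormal and unfavorable | AE | AE |
| Abnormal, then worse | AE | AE |
| Abnormal, then improved or normal | AE | Not an AE |
| No change | Not an AE | Not an AE |

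The documents disagree in the third row. This follows from the wording alone.

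**Step 2. Look for a limit elsewhere in the SAP.** The SAP has no AE definition of its own. SAP section 9 lists physical examination as a safety parameter without qualification. SAP section 15 lists each result as normal or abnormal, with its clinical significance, so the data needed to separate better from worse are available, but 14.6 does not use them.

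**Step 3. Follow the record to the tables.** SAP 14.4 tabulates the number and percent of Safety population subjects reporting AEs, by system organ class, preferred term, severity and relationship. A resolved finding recorded under 14.6 would be counted there.

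**Step 4. Test whether Tanner stage falls under the rule.** SAP 14.6 compares baseline with end of study.

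- The examination is complete at screening (Protocol 8.6.1) and at end of treatment (8.6.11 for Part A, "Physical Examination-complete"; 8.6.18 for Part B). Its stated minimum does not name Tanner stage.
- Tanner stage is a separate item in each of those visit lists.
- A directed examination takes place on Day 0, but Protocol 8.6.2 and Table 1 schedule no Tanner staging that day.
- SAP Table 5 classes the complete examination as baseline and safety, and Tanner staging as efficacy. Tanner stage is absent from the safety list in SAP section 9.

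On the other side, the complete examination's content is only a minimum, SAP 8.1.7 describes Tanner stages as part of the directed examination, and 14.6 does not exclude them. The overlap is left open, but nothing says that Tanner change is an AE.

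**Step 5. Try to size it.** The count needs the number of children with an end-of-study examination and the proportion of them with a baseline finding that improves. Neither is given. Planned enrolment is about 60, while Protocol 9.1 and SAP 6.7 expect a final sample of 25 to 50. Protocol 8.2.4 also asks for end-of-treatment assessments in children who stop early. No rate of resolved findings or of Tanner regression appears in either document.

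**The case against.** The strongest reply is that the protocol governs AE recording. Investigators apply Protocol 8.5.4.1 and 8.5.5, and the AE list is compiled from what they enter in the eCRF (Protocol 9.2.6). The SAP tables count reported AEs, and no SAP step derives AEs from examination data. SAP section 4 assumes that the reader knows the protocol. On this view an improved finding becomes an AE only if someone sets the protocol definition aside.

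Much of this stands. It means that inflated AE tables are a consequence of following 14.6, not a certainty. It does not rescue the sentence. Either 14.6 is operative and adds events that the protocol excludes, or it has no effect and misdescribes how AEs arise. Both call for correction. Assuming familiarity with the protocol is also not a statement that the protocol prevails over a contrary SAP rule.

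A reader might go further and infer that pubertal regression, the intended effect of treatment, would be tabulated as harm, with the same Tanner data shown as benefit in one table and as AEs in another. The documents do not support that as a finding. The passage that names Tanner stages describes the directed examination, whereas the end-of-treatment examination is complete, and the SAP keeps Tanner stage apart as efficacy throughout.

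**Conclusion.** The point holds as a conflict between SAP 14.6 and Protocol 8.5.4.1 and 8.5.5 over resolved or improved examination findings. It is a wrong rule, not a missing detail: applied as stated, it gives an AE count that the protocol's definition does not allow.

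Its reach is limited. It concerns changes between baseline and end of study, and it affects only AE recording and the safety tables. The primary endpoint, the 80% efficacy criterion and the sample size do not depend on it. No number of extra AEs can be given. Multiplying the planned enrolment of 60 by a guessed rate of improvement would use a rate found in neither document and the wrong denominator.

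The conclusion assumes that the sentence is read literally and that no unpublished instruction to sites or programmers overrides it. Counting Tanner regression as an AE remains a possible reading that one clause would close; the conclusion does not rely on it.

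**What to change.** Replace the last sentence of SAP 14.6 with:

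> New or worsened physical examination findings that meet the adverse event definition in Protocol 8.5.4.1 are reported as adverse events; changes in Tanner stage and menses are analysed as efficacy unless the investigator reports them as adverse events under that definition.

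Three tempting additions should be left out, because each is narrower than the protocol and could under-report harm:

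- **A clinical-significance test for all examination findings.** The protocol applies that test to laboratory findings; 8.5.4.1 does not apply it to unfavorable signs in general.
- **A restriction to findings after the first dose.** The protocol collects AEs from consent and reports pre-dose events as not treatment-emergent.
- **A flat exclusion of Tanner stage.** This could remove an unfavorable pubertal change that an investigator judges to be an AE.

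The cost is one SAP sentence and an entry in the SAP change log. No new data, visits or analyses are needed.

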### **15. TABLES, LISTINGS AND FIGURES**

Organized listings of data will be provided that show by variable the values for each subject. At the medical writer's direction, listings that show specified variables by subject may be created. Selected details involving the listings are found below. Mock headings that specify the obtained and derived variables that are to be placed in listings will be included with this SAP.

- Inclusion and exclusion criteria will be provided in separate data listing by subject.
- A summary of observed values (all vital sign measurements, bone age, and tanner stage) for each scheduled visit will be presented in the listings.
- Physical examination body system, results (normal, abnormal), date and time of evaluation, clinical significance and a comment describing the abnormality and clinical significance of the abnormality will be in the listings.
- Clinical laboratory test results will be presented in the data listings. Values that are outside of the reference range will be flagged.
- All qualitative pregnancy test results (positive, negative) will be provided with date and study day of collection in the listings.
- All literal and MedDRA adverse events will be in the listings. System organ class, preferred term, severity and relationship to treatment will be presented.

Mock tables that present the analyses planned for this study and mock figures that contain the planned exhibits will be formulated and included with this SAP.

Appendix 5 will be added to this SAP and will contain mock tables, listings and figures.

### **16. BASELINE VALUES OF DROPPED SUBJECTS**

If the study terminates with Part A, subjects not available for primary efficacy evaluation at six months will be compared to available subjects on key baseline parameters as directed by the medical writer. If Part B is invoked, subjects not available for primary efficacy evaluation at 21 months will be compared to available subjects on key baseline parameters as directed by the medical writer.

### **17. DATA SAFETY MONITORING BOARD**

An Independent Data Safety Monitoring Board (DSMB) will be used to a) monitor safety throughout the study and b) determine whether Part B of the study is to be invoked. DSMB

responsibilities will be specified in a DSMB charter. The statistician will prepare data reports as directed in the charter and will be available to the DSMB.

## 18. CONVENTIONS

Unless otherwise indicated by prevailing considerations, the following conventions will be used.

### 18.1. Reporting Conventions

- All tables and data listings will be developed in Landscape Orientation, unless presented as part of the text in a CSR.
- Figures will be presented in Landscape Orientation, unless presented as part of the text in a CSR.
- Legends will be used for all figures with more than one variable or item displayed.
- Figures will be presented in color with treatment groups distinguished by different symbols and colors. Lines in figures should be wide enough to view the line after being photocopied.
- Specialized text styles, such as bolding, italics, borders, shading, superscripted and subscripted text will not be used in tables, figures, and data listings unless they add significant value to the table, figure, or data listing.
- Only standard keyboard characters should be used in tables and data listings. Special characters, such as non-printable control characters, printer specific, or font specific characters, will not be used on a table, figure, or data listing. Hexadecimal character representations are allowed (e.g., $\mu$ , $\alpha$ , $\beta$ ).
- All titles will be centered on a page. The ICH numbering convention is to be used for all tables, figures, and data listings.
- All footnotes will be left justified and the bottom of a page. Footnotes must be present on the page where they are first referenced. Footnotes should be used sparingly and must add value to the table, figure, or data listing. If more than four footnote lines are planned then at the programmer's discretion a cover page may be used to display footnotes.
- Missing values for both numeric and character variables will be presented as blanks in a table or data listing. A zero (0) may be used if appropriate to identify when the frequency of a variable is not observed.
- All date values will be presented as YYYY-MM-DD (e.g., 2013-05-17) ISO 8601 format.
- All observed time values will be presented using a 24-hour clock HH:MM:SS format (e.g., 01:35:45 or 11:26). Seconds should only be reported if they were measured as part of the study, also in ISO 8601 format.

- Time durations will be reported in mixed HHh MMm SSs notation (e.g., 5h 32m, or 27h 52m 31s). The use of decimal notation to present (display) time durations should be avoided (e.g. 0.083h = 5m) unless it is necessary to show the computation of time differences in a table, figure, or data listing, in which case both notations may be used to display the time duration.
- All tables, figures, and data listings will have the Table, Listing, or Graph status (DRAFT, FINAL), and a date/time stamp on the bottom of each output.
- All analysis programs developed for a table, figure, or data listing display will be self-contained to facilitate transfer of programs to multiple computing environments and transfer to a regulatory agency (if requested).

## 18.2. Population Summary Conventions

- Population(s) represented on the tables or data listings will be clearly identified in the last title of the Table as “Population: <name of population>” and will be identical in name to that identified in the protocol or SAP.
- Consistent terminology will be used to define and identify a population.
- Sub-population(s) or special population(s) descriptions will provide sufficient detail to ensure comprehension of the population (e.g., FAS Females, Per-Protocol Males >60 years of age) used for analysis in a table or figure.
- Population sizes may be presented for each treatment or dosing category as totals in the column header as (N=xxxx), where appropriate.
- Population sizes shown with summary statistics are the samples sizes (n) of subjects with non-missing values.
- All population summaries for categorical variables will include all categories that were planned and for which the subjects may have had a response. Percentages corresponding to null categories (cells) will be suppressed.
- All population summaries for continuous variables will include at least N, mean, SD, minimum, and maximum. Other summaries (e.g. number missing, median, quartiles, 5%, 95% intervals, CV or %CV) may be used as appropriate.
- All percentages are rounded and reported to xx.x%. A percentage of 100% will be reported as 100%. Any computation that results in 0% will be reported as 0% unless otherwise indicated.

